9.2 Cycle Delay and Dose Modification Guidelines

Within a week prior to the first day of each new treatment cycle, the patient will be evaluated for possible toxicities that may have occurred due to previous doses. Toxicities will be assessed according to the National Cancer Institute Common Terminology Criteria for Adverse Events (NCI CTCAE), version 4.0. Cycle delays and dose modifications will be made based on the toxicity experienced during the previous cycle of therapy or the ones encountered on any of the treatment days. Doses of study drug that need to be held WITHIN a cycle are skipped and will not be made up later in the cycle.

9.2.1. Instruction for Initiation of a New Cycle

A new course of treatment may begin on the scheduled Day 1 of a new cycle if:

- The ANC is $\geq 1,000/\mu\text{L}$
- The platelet count is $\geq 50,000/\mu\text{L}$
- Hemoglobin is $\geq 8\text{g/dL}$
- Any drug-related side effect rash, allergic reaction/hypersensitivity, sinus bradycardia/

**MEMORIAL SLOAN-KETTERING CANCER CENTER
IRB PROTOCOL**

IRB#: 11-107A(12)

other cardiac arrhythmia adverse event, dyspepsia, gastritis, gastric or duodenal ulcer or confusion or mood alterations that may have occurred has resolved to \leq grade 1 severity

- Any other drug-related adverse events that may have occurred have resolved to \leq grade 2 severity.

If these conditions are not met on Day 1 of a new cycle, the subject will be evaluated weekly and a new cycle of lenalidomide will not be initiated until the toxicity has resolved as described above. If the toxicity does not resolve after four weeks of delay, the patient will be taken off study.

If dosing of lenalidomide was halted during the previous cycle and was restarted with a one-level dose reduction without requiring an interruption for the remainder of the cycle, then that reduced dose level will be initiated on Day 1 of the new cycle.

If dosing of lenalidomide was omitted for the remainder of the previous cycle or if the new cycle is delayed due to toxicity newly encountered on the scheduled Day 1, then the new cycle will be started with dose modifications as described in Section 9.2.3.

9.2.2. Lenalidomide Dose Reduction Guidelines

Table 3: Dose Modification for Lenalidomide		
NCI CTC v3.0 Toxicity Grade	Day 2 – 14 of Cycle	\geq Day 15 of Cycle
Grade 3 neutropenia associated with fever (temperature $\geq 38.5^{\circ}\text{C}$ or Grade 4 neutropenia)	
 Hold (interrupt dose) Follow CBC weekly If neutropenia has resolved to \leq grade 2 prior to Day 21, restart at next lower dose level and continue the cycle until Day 21. 	
 Omit lenalidomide for remainder of the cycle If neutropenia is the only toxicity for which a dose reduction is required, G-CSF may be used and the dose maintained for the next cycle at the treating physician's discretion
Thrombocytopenia \geq Grade 3 (platelet count $< 50,000/\text{mm}^3$)	
 Hold (interrupt dose) Follow CBC weekly If thrombocytopenia resolves to \leq grade 2 prior to Day 21, restart at next lower dose level and continue the cycle until Day 21 Hold anticoagulation for platelet count $< 50,000/\text{mm}^3$ 	
 Omit lenalidomide for remainder of cycle Hold anticoagulation for platelet count $< 50,000/\text{mm}^3$

MEMORIAL SLOAN-KETTERING CANCER CENTER
IRB PROTOCOL

IRB#: 11-107A(12)

Anemia \geq Grade 3 (Hgb < 8g/dL)	
 · Hold (interrupt dose) · Follow CBC weekly · If anemia resolves to \leq grade 2 prior to Day 21, restart at next lower dose level and continue the cycle until Day 21 	
 · Omit lenalidomide for remainder of cycle
Non-blistering rash Grade 3	
 · Hold (interrupt dose) · Follow weekly · If the toxicity resolves to \leq grade 1 prior to Day 21, restart at next lower dose level and continue the cycle until Day 21 	
 · Omit lenalidomide for remainder of cycle
Non-blistering rash Grade 4	
 · Discontinue lenalidomide study drug 	
 · Discontinue lenalidomide study drug
Desquamating (blistering) rash - any Grade	
 · Discontinue lenalidomide study drug 	
 · Discontinue lenalidomide study drug
Erythema multiforme \geq Grade 3	
 · Discontinue lenalidomide study drug 	
 · Discontinue lenalidomide study drug
Sinus bradycardia/other cardiac arrhythmia Grade 2	
 · Hold (interrupt) dose · Follow at least weekly · If toxicity resolves to \leq grade 1 prior to Day 21, restart at next lower dose level and continue the cycle until Day 21 	
 · Omit lenalidomide for remainder of cycle
Sinus bradycardia/other cardiac arrhythmia \geq Grade 3	
 · Discontinue lenalidomide study drug 	
 · Discontinue lenalidomide study drug
Allergic reaction or hypersensitivity Grade 2-3	
 · Hold (interrupt) dose · Follow at least weekly · If toxicity resolves to \leq grade 1 prior to Day 21, restart at next lower dose level and continue the cycle until Day 21 	
 · Omit lenalidomide for remainder of cycle
Allergic reaction or hypersensitivity Grade 4	
 · Discontinue lenalidomide study drug 	
 · Discontinue lenalidomide study drug

**MEMORIAL SLOAN-KETTERING CANCER CENTER
IRB PROTOCOL**

IRB#: 11-107A(12)

Venous thrombosis/embolism \geq Grade 3
	
 Hold (interrupt dose) and start anticoagulation; restart at investigator's discretion (maintain dose level) 	
 Omit lenalidomide for remainder of cycle

Other non-hematologic toxicity assessed as Lenalidomide-related \geq Grade 3
	
 Hold (interrupt dose) Follow at least weekly If toxicity resolves to \leq grade 1 prior to Day 21, restart at next lower dose level and continue the cycle until Day 21 	
 Omit lenalidomide for remainder of cycle

Hyperthyroidism or hypothyroidism
	
 Omit lenalidomide for remainder of cycle, evaluation etiology, and initiate appropriate therapy See Instructions for Initiation of a New Cycle and reduce the dose of lenalidomide by 1 dose level 	
 Omit lenalidomide for remainder of cycle, evaluation etiology, and initiate appropriate therapy See Instructions for Initiation of a New Cycle and reduce the dose of lenalidomide by 1 dose level

9.2.3. Lenalidomide Dose Reduction Levels

Lenalidomide Dose Reduction Steps	
Starting Dose	25 mg daily for 21 days every 28 days
Dose Level -1	20 mg daily for 21 days every 28 days
Dose Level -2	15 mg daily for 21 days every 28 days
Dose Level -3	10 mg daily for 21 days every 28 days
Dose level -4	5 mg daily for 21 days every 28 days
Dose level -5	Discontinue lenalidomide

9.2.4 Dexamethasone Dose Reduction Guidelines

Table 4: Dose Modification for Dexamethasone		
Dyspepsia	\geq Grade 3	
 Hold (interrupt) dexamethasone until \leq grade 1 Reduce dexamethasone by 1 dose level and restart

MEMORIAL SLOAN-KETTERING CANCER CENTER
IRB PROTOCOL

IRB#: 11-107A(12)

Gastritis, gastric or duodenal ulcer	≥ Grade 3	
 · Hold (interrupt) dexamethasone until ≤ grade 1 · Reduce dexamethasone by 1 dose level and restart
Edema	≥ Grade 3	
 · Reduce dexamethasone by 1 dose level · Use diuretics, as needed
Confusion or mood alternations	≥ Grade 2	
 · Hold (interrupt) dexamethasone until ≤ grade 1 · Reduce dexamethasone by 1
Muscle weakness	≥ Grade 3	
 · Reduce dexamethasone by 1 dose · If symptoms persist, continue to reduce dexamethasone by 1 dose level, as needed
Hyperglycemia	≥ Grade 3	
 · Reduce dexamethasone by 1 dose level · Treat with insulin or oral hypoglycemics, as needed
Acute pancreatitis	≥ Grade 3	
 · Discontinue dexamethasone and take patient off study
Other non-hematologic toxicity assessed as dexamethasone related	≥ Grade 3	
 · Hold dexamethasone for remainder of cycle · Reduce dexamethasone by 1 dose level

9.2.5 Dexamethasone dose reduction levels

Dexamethasone Dose Reduction Steps	
Starting Dose	40mg weekly on days 1, 8, 15 and 22 of each 28-day cycle
Dose Level -1	20mg weekly on days 1, 8, 15 and 22 of each 28-day cycle

MEMORIAL SLOAN-KETTERING CANCER CENTER
IRB PROTOCOL

IRB#: 11-107A(12)

Dose Level -2	12mg weekly on days 1, 8, 15 and 22 of each 28-day cycle
Dose Level -3	4mg weekly on days 1, 8, 15 and 22 of each 28-day cycle

9.3 Supportive Care

- Monthly IV bisphosphonates (either Zometa or Pamidronate according to institutional preference) may be initiated or continued according to local institutional practice.
- Patients can receive filgrastim or pegylated filgrastim for an ANC < 109/L.
- Radiation therapy is not permitted concurrently in this trial.
- Transfusion thresholds for blood product support should be per institutional guidelines. All blood products will be irradiated.
- Treating physicians should be aware of the increased risk of DVT and PE with lenalidomide when combined with dexamethasone and have heightened vigilance regarding this possible toxicity. There is no clear evidence that the risk of DVT is increased on lenalidomide alone. Aspirin 325 mg/day orally should be administered during lenalidomide therapy when associated with dexamethasone unless the patient is treated with alternate prophylaxis of either low molecular weight heparin or Coumadin. This will be left to the discretion of the treating physician.
- Concurrent use of erythropoietin requires full anticoagulation of patients with therapeutic doses of LMWH or Coumadin. Anticoagulation should be held for platelet counts <50,000/mm³.
- Prophylaxis therapy should be added when patient start dexamethasone including fluconazole 100mg PO daily, Bactrim DS, three days a week, and a PPI daily.

10.1 EVALUATION DURING TREATMENT/INTERVENTION

During the intervention period, the patients will be assessed in the clinic before initiation of every cycle and will have the following evaluation done before every cycle, within one week of day 1 of the cycle:

- History and physical exam including vital signs, weight, and performance status.
- Review medication diary. Patients will be given a medication diary at the beginning of each cycle to document lenalidomide administration.
- CBC with differential and platelet count
- Comprehensive metabolic panel with LDH and phosphorus. The comprehensive metabolic panel includes albumin, alkaline phosphatase, ALT, AST, BUN, calcium, carbon dioxide, chloride, creatinine, glucose, potassium, sodium, total bilirubin, and total protein.

MEMORIAL SLOAN-KETTERING CANCER CENTER IRB PROTOCOL

IRB#: 11-107A(12)

- Myeloma response assessment: Including serum studies (Protein electrophoresis, Quantitative Immunoglobulins, Immunofixation and free light chain assay) and 24h urine studies (protein electrophoresis, Total protein, Immunofixation, and creatinine clearance)
- Toxicity assessment using CTCAE 4.0: maximum grade and status of \geq grade 2 adverse events.
- Bone marrow aspiration and biopsy to be performed only when indicated to document CR or progression.
- Radiological evaluation when needed to document response or progression.
- Required evaluation for Lenalidomide: Pregnancy test, serum or urine HCG (sensitivity of at least 50 mIU/mL) for female of childbearing potential (FCBP):
- FCBP with regular or no menstruation must have a pregnancy test weekly for the first 28 days and then every 28 days while on therapy (including breaks in therapy); at discontinuation of lenalidomide and at Day 28 post the last dose of lenalidomide. Females with irregular menstruation must have a pregnancy test weekly for the first 28 days and then every 14 days while on therapy (including breaks in therapy), at discontinuation of lenalidomide and at Day 14 and Day 28 post the last dose of lenalidomide (Appendix B).
- All patients must be counseled about pregnancy precautions, risks of fetal exposure and other risks. The counseling must be done on Day 1 of each cycle (or at a minimum of every 28 days) and at drug discontinuation. See Appendix: Education and Counseling Guidance Document. A Lenalidomide Information Sheet (Appendix D) will be supplied with each medication dispense.

The same evaluation will be repeated at the end of study, within 4 weeks of the last dose. On day 15 of each cycle the patient will have a CBC. Pre-screening assessments may be used for Cycle 1/Day 1 if they were complete within 7 days of initiation of cycle 1.

Correlative Studies

Patients who give their consent to optional sample collection for research studies will have blood samples (6 CPT tubes and 1 SST tube) collected for research on immune function prior to lenalidomide dose escalation, Cycle 1, Day 15 (+/- 3 days) following dose escalation, prior to addition of dexamethasone, and Day 15 (+/- 3 days) following the addition of dexamethasone. Research blood samples will be collected during the time of standard toxicity evaluation during lenalidomide therapy. The standard treatment schedule includes a 7 day rest period prior to the administration of the next cycle. Thus, the day 15 time point has been selected to allow for an analysis of immune endpoints during the period when study drug is being administered. In addition, 5-7 cc of bone marrow aspirate (in EDTA) will be collected at the time of registration. Samples will be sent to MSKCC for central processing, cataloging, and storage.

**MEMORIAL SLOAN-KETTERING CANCER CENTER
IRB PROTOCOL**

IRB#: 11-107A(12)

Time Point	Window for Collection	Tubes
Baseline/pre-lenalidomide escalation	Day -7 (consent must be signed) through Cycle 1/Day 1	5-7cc bone marrow aspirate (6) CPT tubes (1) SST tube
Cycle 1/Day 15	Cycle 1/ Day 15 (+/- 3 days)	(6) CPT tubes (1) SST tube
Pre-dexamethasone addition	Between asymptomatic progression and addition of dexamethasone	(6) CPT tubes (1) SST tube
Day 15 post-dexamethasone addition	Day 15 (+/- 3 days) post-dexamethasone addition	(6) CPT tubes (1) SST tube

Schedule of Study Assessments

Required Studies / Testing	Pretreatment within 8 weeks	Pretreatment within 28 days	Pretreatment within 14 days	Before Every Cycle (within 1 week of day 1)⁸	On day 15 of each cycle	End of Study (Within weeks of dose)
Informed Consent		X				
History and Physical Examination (Height ⁷ and Weight)			X	X		X
Vital Signs			X	X		X
Review medication diary				X		X
Toxicity assessment			X	X		X
Pregnancy Test ²			X ³	X ³		X ³
Register patient into the Revlimid REMS™ program			X			
Performance Status (Karnofsky Performance Score or ECOG)			X	X		X
CBC with Differential and platelet count			X	X	X	X
Comprehensive Metabolic Panel ⁶			X	X		X
LDH, Phosphorus			X	X		X
B2 Microglobulin, Albumin			X	X		X
INR/PTT, BNP, troponin			X			
Hepatitis A, B, and C and HIV 1/2 test	X					
Serum Multiple Myeloma Disease Assessment · Protein electrophoresis · Quantitative			X	X		X

**MEMORIAL SLOAN-KETTERING CANCER CENTER
IRB PROTOCOL**

IRB#: 11-107A(12)

Immunoglobulins · Immunofixation · Serum Free Light Chain Assay						
24 hour Urine Multiple Myeloma Disease assessment · Protein electrophoresis · Immunofixation · Total volume, total protein · Creatinine clearance			X	X ⁵		X
EKG			X			
Skeletal Survey	X ^{1,10}					X
PET scan or total body MRI if available (optional)	X ¹					
Bone Marrow Aspirate and Biopsy for · Morphology · Cytogenetics and FISH analysis · Tissue Banking	X ¹					X ⁴
Optional Research Blood ⁹		X				
Optional Research Bone Marrow Aspirate	X					

¹ To be performed within 8 weeks of registration.

² Pregnancy tests for females of childbearing potential: A female of childbearing potential (FCBP) is a sexually mature female who: 1) has not undergone a hysterectomy or bilateral oophorectomy; or 2) has not been naturally postmenopausal for at least 24 consecutive months (i.e., has had menses at any time in the preceding 24 consecutive months).

³ Pregnancy tests must occur within 10 – 14 days and again within 24 hours prior to prescribing lenalidomide for Cycle 1 (prescriptions must be filled within 7 days). FCBP with regular or no menstruation must have a pregnancy test weekly for the first 28 days and then every 28 days while on therapy (including breaks in therapy); at discontinuation of lenalidomide and at Day 28 post the last dose of lenalidomide. Females with irregular menstruation must have a pregnancy test weekly for the first 28 days and then every 14 days while on therapy (including breaks in therapy), at discontinuation of lenalidomide and at Day 14 and Day 28 post the last dose of lenalidomide (see Appendix: Risks of Fetal Exposure, Pregnancy Testing Guidelines and Acceptable Birth Control Methods)

⁴ Unilateral bone marrow aspirate and biopsy will be done only to confirm complete remission in patients with negative biochemical evidence of disease.

⁵ If the baseline urine paraprotein level is less than 200mg/24hrs, the UPEP is not required.

⁶ Albumin, Alkaline Phosphatase, ALT, AST, BUN, Calcium, Carbon dioxide, Chloride, Creatinine, Glucose, Potassium, Sodium, Total Bilirubin, Total Protein

⁷ Height only required during pretreatment evaluation.

⁸ Pre-screening assessments may be used for Cycle 1/Day 1 if they were complete within 7 days of initiation of cycle 1.

⁹ Optional blood will be collected prior to dose escalation (baseline), 15 days (+/- 3 days) post dose escalation, prior to addition of dexamethasone, and 15 days (+/- 3 days) post addition of dexamethasone.

¹⁰ A skeletal survey is only required for screening if PET scan was not completed.

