1.7 Study Schema

2.0 OBJECTIVES AND SCIENTIFIC AIMS

Primary objective:

- To determine the overall response rate (CR, VGPR, PR, and MR) after 6 months of lenalidomide intensification administered initially at a dose of 25 mg orally days 1 to 21 of a 28 day-cycle, with or without the addition of dexamethasone, in patients with multiple myeloma found to have *asymptomatic* progression of their disease while on maintenance lenalidomide dose of 15mg mg daily or less.

Secondary objectives:

- To determine rates of \geq Grade 2 toxicity according to the Common Terminology Criteria for Adverse Events (CTCAE) Version 4.0
- To determine the overall response rate (CR, VGPR, and PR) at 6 months from initiation of lenalidomide intensification therapy of lenalidomide given as a single agent.
- To determine progression free survival: The PFS is defined as the time from registration to relapse/progression, death, initiation of non-protocol anti myeloma therapy, loss to follow up or end of study whichever comes first.
- To determine OS: The OS is defined as the time from registration to death, loss to follow-up or the end of the study, whichever comes first. Patients alive at the time of last observation are considered censored.

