4.0 OVERVIEW OF STUDY DESIGN/INTERVENTION

4.1 Design

In this multi-center Phase II single arm trial, 53 patients fulfilling the eligibility criteria, will be treated with lenalidomide 25 mg PO daily for 21 out of 28 day cycles. The patients' responses to the treatment will be assessed after every cycle. Patients who have asymptomatic POD after 2 cycles will have dexamethasone added at a dose of 40 mg PO weekly. Patients who have at least SD after 2 cycles will continue lenalidomide single agent until asymptomatic POD, at which time they will have dexamethasone added at a dose of 40 mg PO weekly. Patients will be taken off study if they have symptomatic POD after any cycle, if they have any type of POD after dexamethasone is added, or if they do not tolerate the treatment. The patients taken off study due to any type of POD, will be considered failures for the primary response endpoint if progression occurred within 6 months. Patients who are removed from study prior to completing 2 cycles of therapy for reasons other than POD will be considered inevaluable for response and will be replaced. Accrual will continue until 53 evaluable patients have been accrued. Patients who have received any study drug will be evaluated for safety.

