4.2 Intervention

Patients with asymptomatic POD while on maintenance lenalidomide after HDM/ASCT or on continuous/maintenance therapy after initial treatment will be enrolled on this clinical trial and will undergo the following interventions:

- Patients will have their disease fully reassessed in order to establish a new pre-therapy baseline within 2 weeks of initiation of treatment.
- Patients will receive lenalidomide at a dose of 25 mg PO daily for 21 days out of 28-days-cycles.
- Patient will be evaluated for response and toxicity after every cycle.
- Patients with at least SD after 2 cycles of lenalidomide will continue on lenalidomide until asymptomatic POD, at which time dexamethasone will be added at a dose of 40 mg PO weekly at the next cycle.

MEMORIAL SLOAN-KETTERING CANCER CENTER IRB PROTOCOL

IRB#: 11-107A(12)

[figure not shown]
- Patients with asymptomatic POD after 2 or more cycles of lenalidomide will have dexamethasone added to lenalidomide at a dose of 40 mg PO weekly at the next cycle.
- Patients with further asymptomatic POD after at any cycle of lenalidomide and dexamethasone will be taken off study and treated at the discretion of the treating physician. Note that further POD after the addition of dexamethasone will be determined compared to the new M spike baseline just prior to the addition of dexamethasone.
- Note that patients with symptomatic POD at any point in time during treatment will be taken off study.

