14.0 BIOSTATISTICS

The primary objective of this study is to estimate overall response rate (\geq PR) to lenalidomide intensification with or without dexamethasone at 6 months. A single stage design that differentiates between response rates of 15% and 30% will be used to assess efficacy of lenalidomide intensification with or without dexamethasone.

The probabilities of a type I error (falsely accepting a non-promising therapy) and type II error (falsely rejecting a promising therapy) are set to 0.10 and 0.10, respectively. The null hypothesis response rate is based on the response rates ranging from 12.5% to 16.4% to the standard of care therapy in patients previously exposed to thalidomide who have relapsed or refractory disease (reference Webber and Dimopoulos papers^{38,39}). A total of 53 patients will be accrued. At the conclusion of the study, if a least 12 of the 53 patients respond by 6 months the treatment will be declared a success. At the end of the study, the response rate will be estimated and a confidence interval will be constructed.

We expect to accrue 53 patients in two years with approximately 10-15 patients accrued from MSKCC and the remaining patients accrued from the other centers.

The incidence of toxicities of grade 2 or higher toxicities (CTCAE version 4.0), the incidence of probable viral fungal and bacterial infections, and the incidence of treatment-related mortality, i.e., from causes other than relapse or progression, will be recorded for each patient after each cycle and at the end of study visit. Safety data will be described in a variety of ways, both graphically and in tabular form.

Progression free survival is defined as the time from treatment initiation to relapse/progression, death, initiation of non-protocol anti myeloma therapy, or last follow-up. Overall survival is defined as time from treatment initiation until death or last follow-up. Progression free and overall survival will be estimated using the Kaplan-Meier method.

We will estimate the response rate (CR, VGPR, and PR) by 6 months from initiation of lenalidomide intensification of lenalidomide given as single agent. For this calculation, patients who have asymptomatic progression after 2 cycles of lenalidomide and receive dexamethasone will be considered failures.

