16.1.3 Data and Source Documentation Submission Timelines for Participating Sites

Data and source documentation to support data should be transmitted via the EDC system to MSKCC according to the following chart:

	Baseline	During Treatment Cycles	SAE	End of Therapy
SUBMISSION SCHEDULE				
Source Documentation	Within 24 hours (see section 15.1.1)		Within 24 hours (see section 17.2.1 and 17.3); updates to be submitted as available	
CRFs	Within 7 days of visit	within 14 days of the end of cycle		Within 14 days of visit
REQUIRED FOLDERS/FORMS				
Screening Folder	X			
Baseline Folder	X			
Adverse Event Form	X	X	X	X
Concomitant Medications Form	X	X		X
Correlative Form (if applicable)	X	X		X
Cycle (#) Folder		X		
Off Study Folder				X
Serious Adverse Event Form			X	

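### Overall survival is a secondary objective, but the plan schedules no vital-status, progression or next-therapy collection after the end-of-study visit within 4 weeks of the last dose

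*Combined protocol and SAP*

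**What the plan says.** **Endpoint.** Section 2.0 lists OS as a secondary objective: "The OS is defined as the time from registration to death, loss to follow-up or the end of the study, whichever comes first". It adds: "Patients alive at the time of last observation are considered censored". Section 14.0 words it differently: "Overall survival is defined as time from treatment initiation until death or last follow-up". The estimator is given there too: "Progression free and overall survival will be estimated using the Kaplan-Meier method". In both sections, progression, death and the start of non-protocol myeloma therapy all end PFS.

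**Leaving the study.** Section 4.1: "Patients will be taken off study if they have symptomatic POD after any cycle". Section 4.2 repeats it: "Note that patients with symptomatic POD at any point in time during treatment will be taken off study". Sections 1.4, 4.1, 4.2 and 9.1 also remove patients at any POD once dexamethasone has been added, and Section 4.1 removes those who do not tolerate treatment. Asymptomatic POD on lenalidomide alone leads to the addition of dexamethasone, and the patient stays on study.

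**Last data collection.** Section 10.1: "The same evaluation will be repeated at the end of study, within 4 weeks of the last dose". The Schedule of Study Assessments has no column after that visit. In the submission chart for participating sites (Section 16.1.3, submission timelines), the last column is end of therapy and its closing item is the "Off Study Folder". The chart lists no survival or subsequent-therapy form. Section 13.0 gives reasons for removal and describes no follow-up after it.

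**The concern.** Kaplan-Meier treats a censored patient as having the same future risk as those still observed. That is doubtful when observation ends because the disease has progressed beyond what the study treatment can hold. If the schedule is followed literally, a patient who leaves for symptomatic POD is last seen about a month later, and a death after that is never recorded. The curve would then describe survival while on study, under the name of overall survival.

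PFS has a narrower version of the gap. A patient who stops for toxicity before POD can still progress or start another myeloma therapy, and both end PFS, but neither is scheduled to be captured after the end-of-study visit.

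**Working it through.** **1. The plan's own figure.** The plan states no precision, event count or follow-up time for OS. Its only design figure is the response rule, at least 12 responders among 53. Exact binomial gives P(X ≥ 12 | 53, 0.15) = 0.0907 and P(X ≥ 12 | 53, 0.30) = 0.9094, within the stated 0.10 and 0.10 error limits. This rule does not depend on survival follow-up.

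**2. Does any other text supply the follow-up?**
- Section 7.0 says patients will be followed by physicians at the centers.
- Section 16 (Quality Assurance) monitors follow-up and audits follow-up testing.
- Section 18.1 has the consent form describe likely follow-up.
- None of these sets a survival contact, an interval, a duration or a form. The later contacts that are specified concern pregnancy testing and pregnancy outcome.

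**3. Direction.** Bias is upward if the death hazard is higher after leaving than before. The background in Section 3.2.2.1 points that way for symptomatic POD. In the Spanish registry series, median survival was 18 months after insidious relapse and 12 months after symptomatic relapse. In the second series it was 39 months after insidious relapse, against 30 months (skeletal symptoms only) and 18 months (additional symptoms) after classical relapse. Both series predate lenalidomide and bortezomib, so they support a direction, not a size.

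**4. Hypothetical size.** Let patients leave at rate λ, with death hazard h before leaving and μ after, and censoring d = 28/30.44 = 0.92 months after leaving. With a = λ + h:
- True OS: S(t) = e^(−at) + λ[e^(−μt) − e^(−at)]/(a − μ).
- Observed patients in the 28-day window, per patient still on treatment: w = λ[e^((a−μ)d) − 1]/(a − μ).
- Hazard that Kaplan-Meier sees: g = (h + μw)/(1 + w). It then reads about e^(−gt).

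Assume a median time to leaving of 6 months (λ = 0.1155) and a median survival after leaving of 18 months (μ = 0.0385). Neither is a protocol figure for this quantity. At t = 24 months:

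| Hazard before leaving | True OS | Kaplan-Meier reads | Difference (points) |
|---|---|---|---|
| h = μ | e^(−0.924) = 0.397 | g = μ, so 0.397 | 0 |
| h = μ/1.5 = 0.0257 | 0.0337 + 0.1155 × 0.3632/0.1027 = 0.442 | w = 0.111, g = 0.0270, so 0.523 | about 8 |
| h = 0 | 0.0625 + 0.1155 × 0.3344/0.0770 = 0.564 | w = 0.110, g = 0.00382, so 0.912 | about 35 |

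The 1.5 is the ratio 18/12 of the two registry medians, used only as a sample contrast.

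**5. Wider grid.** A simulation of 400,000 patients per scenario used these assumptions:
- median time to leaving 6 or 12 months;
- median survival after leaving 10.8 to 41.8 months;
- hazard before leaving 0 or 0.005 per month;
- administrative follow-up uniform over 12 to 36 months.

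True 24-month OS was 38% to 84%, and Kaplan-Meier with censoring after leaving read 77% to 98%. The overstatement was about 9 to 46 points. Per 53 patients, about 8 to 32 deaths would be seen with follow-up to cut-off, and about 0.6 to 5 without. Every scenario assumes a much lower hazard before leaving than after (at most 0.005 against at least ln 2/41.8 = 0.0166 per month). The uniform direction is therefore a consequence of the assumptions.

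**The case against.** A reader might infer that the plan itself censors OS at progression. It does not. Neither OS definition names POD, stopping treatment or the end-of-study visit as a censoring point. Section 2.0 ends PFS, but not OS, at the start of other therapy, which suggests that OS was meant to run past treatment. The phrase about the end of the study could mean trial closure. Section 13.0 is headed as removal from study but speaks of stopping study drugs, so leaving the study may be loose wording for leaving treatment. This stands, and it makes the finding conditional on collection stopping where the schedule stops. It does not answer the point, because if closure is meant, nothing in the plan brings data up to closure.

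A reader might also infer that every POD ends observation. Asymptomatic POD on lenalidomide alone does not, so many patients are observed beyond their first progression.

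The form evidence has limits. The chart covers participating sites only, while Section 14.0 expects about 10 to 15 of the 53 patients from the lead center. The contents of the off-study forms, the case report forms and the procedure manual are not in the documents. Section 10.1 concerns evaluation during treatment. Sites may well record later deaths, but nothing obliges them to, and uneven capture across centers would be a problem of its own.

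Finally, OS and PFS are descriptive, with no hypothesis or decision rule attached. That limits the consequence and is correct.

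**Conclusion.** The point holds in conditional form. The plan promises an OS estimate and specifies no data after the end-of-study visit from which to make it. If collection stops there, censoring is tied largely to treatment-ending POD, and OS is biased upward provided that mortality is higher after such POD than before. Patients who leave for toxicity or withdrawal are also censored early; for them the direction is less clear. For PFS, the gap concerns patients who leave without POD, and neither its direction nor its size can be stated.

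The documents do not support a numerical size for the OS bias. It is tempting to treat the 18 and 39 month background medians as survival after leaving this study and to call the result protocol-based. Those medians run from insidious relapse, which corresponds to trial entry, not to later departure. The figures above, from 0 to about 46 points at 24 months, are hypothetical and rest on assumed leaving times and hazards. The change should be made because a named secondary objective otherwise lacks its data. The primary response endpoint does not depend on it.

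**What to change.** - In Sections 10.1 and 13.0 and in the 16.1.3 submission chart, separate leaving treatment from leaving the study. A patient who stops study drugs remains in follow-up unless consent to follow-up is withdrawn.
- Add follow-up by chart review or telephone, at an interval chosen by the sponsor. Record vital status, date of last contact or death, date of first POD if not yet reached, and start date of the next anti-myeloma therapy. Apply it at the lead center as well as the participating sites.
- Set a common cut-off date, and define last follow-up and end of the study by it, identically in Sections 2.0 and 14.0, for OS and PFS. The same edit can settle the time origin, which is registration in 2.0 and treatment initiation in 14.0.
- If these data will not be collected, delete OS as an objective or label it survival while on study.

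The cost is one amendment, one form and periodic contact for about 53 patients. It adds no patients and no procedures.
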